3.4.2.2. Trajectory of Depressive and Anxiety Symptoms over Time

We will also examine the trajectory in depressive and anxiety scores over time (baseline, 3-, 6- and 12-months post-randomization), using the EPDS and GAD-7, respectively. To assess change in EPDS scores over time between antenatal and postnatal, a linear mixed model, including the interaction between group and time, will be run. Similar models will be run to compare anxiety scores between the antenatal and postnatal groups as were carried out for depression.

3.4.2.3. Analysis for Secondary Aim 2: Clinical Severity

We are also interested in assessing moderating effects of clinical severity (mild, moderate and severe; see [Appendix 2](#) for cut-off values and severity classification for outcomes) on the comparative effectiveness of the two delivery modes on depressive and anxiety symptoms at 3-, 6- and 12-months post randomization.

This will involve the use of linear mixed models. Using a non-inferiority margin of 10%, 10% dropout, and an alpha of 0.05, we require 44 participants³⁸. Mothers will be taken as a random effect and the models will include a treatment-by-time interaction term. Other potential moderators will be explored such as age, ante or postnatal enrollment, patient preference, white/BIPOC, and trauma symptoms. The same set of analyses as above will be conducted for anxiety symptoms (GAD-7), disability scores, quality of life, and client satisfaction.

3.4.2.4. Analysis for Secondary Aim 3: Perinatal Period and Child Development

Another secondary aim is to explore whether the timing of the treatment (antenatal vs. postnatal) influences child mental development at 6 to 24 months post childbirth.

All child outcomes, including child mental development and the provision of psychosocial stimulation by the mother, will be compared between two groups (antenatal vs. postnatal) at 6-24 months post childbirth using a two-sample two-sided t-test. We will require a sample of 393 participants in each of the two groups to detect a mean clinically-significant change of 3.0 units with 80% power and an alpha of 0.05. Similar comparisons will be run between the primary comparison arms (SP vs NSP; in-person vs telemedicine). Sensitivity analyses will be carried out excluding those who dropped out prior and after first session to see if the results are comparable to the entire study group. We will adjust for time since treatment by including it as a variable in the regression model comparing antenatal vs. postnatal.

We will examine the hypothesis of whether the subset of mothers (up to 75% of the sample) who receive the antenatal treatment will benefit more in terms of improved child outcomes at 6-24 months than mothers who receive postnatal treatment. A 2-group comparison of 393 per group (antenatal vs. postnatal) and an assumed mean on any Bayley IV²⁷ raw subscale score of 100, SD=15 to assess child mental development will provide 80% power, with an alpha of 0.05 to detect a mean clinically-significant change of 3.0 units. Raw and standardized Bayley IV scores of

the two groups' children (antenatal vs. postnatal) at 12 months will be compared using a two-sided, two-sample t-test.

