Intervention Costs	A survey of costs associated with the intervention	Self-reported and health records, related to the economic evaluation portion of the study
Treatment: Measured at every	session during treatment, unless otherwise indicated	
Dosage	Treatment Log 	Frequency of Sessions Attended
Therapy Quality****	Quality of Healthy Activity Program (Q-HAP)52	Mean continuous score of treatment-specific BA skills (0-4) and general counseling skills (0-4)
Session Depressive / Anxiety	Session-by-session EPDS  and GAD-7  scores	Mean continuous score of a 10-item scale (0-30) on EPDS and of a 7-item scale (0-21) on GAD-7
Homework Adherence	Treatment Log 	Mean continuous score of a 1-item question (0-2)
Adverse or Serious AEs	Anytime an Adverse Event (AE) or Serious AE occurs	Any event that represents a series threat to the safety of the mother or her child (see Appendix D)
Health Service Utilization	Health Service Utilization Form 	Total score of a 16-item scale (0-32)
List of Medications	List of Medications	Self-reported list of medications
COVID-19 Exposure	1-item question on COVID-19 exposure	Self-reported
Child: Measured at 6 to 24-more	nths post-child birth unless otherwise indicated	
Birth weight & Length	Retrieved from hospital chart or self-report†	Assessed at birth

Breastfeeding	Whether breastfeeding and if stopped age stopped.54	Total Number of Months (0-12)
Psychosocial Stimulation	Home Observation Measurement Evaluation 	Total score of a 45-item checklist
Mental Development	Bayley Mental Development Scales IV 	Mean continuous score of cognitive, receptive and expressive language development

\* Assessment period will be extended to account for post-treatment outcomes when there are perinatal-related interruptions to treatment (e.g., giving birth, obstetrical complications, COVID-19); \*\*Only at baseline; \*\*\*Measured at 3-months post-randomization only; \*\*\*\*Randomly selected for supervision, rated by self, peers, expert supervisor; †Self-report will be used when hospital charts are outside of the recruiting site; Measured at baseline for participants consented after addition of measure to baseline questionnaire, measured at 12-months post-randomization for those who completed baseline before addition of measure; Deasured once at 3-, 6- or 12-months post-randomization.

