In addition, we will run a linear regression model with mode, agent and a mode by agent interaction term to assess whether an interaction between mode and agent exists. In the unlikely event that randomization was not able to reduce bias by balancing out confounders, we will assess for confounding. This will be carried out by assessing each potential confounder individually in relation to the key predictor (mode or agent) and seeing if the potential confounder impacts the parameter estimate of the key predictor using the 10% change in estimate approach. The potential confounder would also need to be significantly related to the EPDS score outcome. Should any confounders exist, they'll will be included in all of the previously mentioned analyses. Rules on the number of variables allowed in a multivariable model will be followed. The rule on number of variables in a linear regression is to take the total number of observations divided by 10. Given our trial sample size, we will not have any concerns with overfitting our linear model for our covariates of interest (education level, marital status, ethnicity, baseline severity and chronicity, timing of treatment, compliance, perceived support and medication).

Our study statistician and two independent methodological consultants have reviewed and approved this plan of analysis.

**3.5.2. Secondary Analysis.** In our secondary analysis, we are interested in: i) assessing the trend in EPDS scores over time (baseline, 3, 6- and 12-months post-randomization) between

groups (telemedicine vs in-person, and specialist vs NSP). This will involve the use of linear mixed models adjusting for possible covariates including baseline depression symptoms, medication, treatment dosage, and child age when assessing child outcomes. Mothers will be taken as a random effect and the models will include a treatment- by- time interaction term; ii) the same set of analyses will be conducted for anxiety symptoms (GAD-7). All child outcomes, including child mental development and the provision of psychosocial stimulation by the mother, will be compared between two groups (antenatal vs. postnatal) at 6-24 months post-childbirth using a two-sample two-sided t-test. Sensitivity analyses will be carried out excluding those who dropped out after first session to see if the results are comparable to the entire study group. No interim analyses will be carried out.

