Health Service Utilization	Health Service Utilization Questionnaire (HSU-Q) ²³	Total score of a 16-item scale (0-32)
List of Medications	List of Medications	Self-reported list of medications
Child: Measured at 6 to 24-months post-childbirth unless otherwise indicated		
Birth Weight & Length	Retrieved from hospital chart or self-report [†]	Assessed at birth
Breastfeeding	Whether breastfeeding and if stopped age stopped ⁷	Total Number of Months
Psychosocial Stimulation	Home Observation Measurement Evaluation (HOME) ²⁶	Total score of a 45-item checklist
Child Mental Development	Bayley Child Mental Development Scales IV ²⁷	Mean continuous score of cognitive, receptive and expressive language development

* Assessment period will be extended to account for post-treatment outcomes when there are perinatal-related interruptions to treatment (e.g., giving birth, obstetrical complications, COVID-19);

Only at baseline; *Measured at 3-months post-randomization only; ****Randomly selected for supervision, rated by self, peers, expert supervisor; ¥Also measured during treatment; [†]Self-report will be used when hospital charts are external to the recruiting site.

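### Arm comparisons of birth weight and length are diluted by women enrolled after the birth, and breastfeeding months need an analysis that handles censoring (minor)

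*SAP*

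**What the plan says.** SAP 3.4.2.4 sets the scope ("All child outcomes, including child mental development and the provision of psychosocial stimulation by the mother, will be compared between two groups (antenatal vs. postnatal") and the method: "at 6-24 months post childbirth using a two-sample two-sided t-test". It then adds: "Similar comparisons will be run between the primary comparison arms (SP vs NSP; in-person vs telemedicine"). Protocol 3.5.2 has the antenatal vs postnatal test in nearly the same words: "will be compared between two groups (antenatal vs. postnatal) at 6-24 months post-childbirth using a two-sample two-sided t-test".

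The Child block of SAP Table 2 is headed "Child: Measured at 6 to 24-months post-childbirth unless otherwise indicated". It holds four entries: birth weight and length ("Assessed at birth"), breastfeeding, HOME and Bayley. SAP 1.4 describes Table 2 as the list of primary and secondary outcomes. The breastfeeding item is "Whether breastfeeding and if stopped age stopped", expressed as a number of months with no upper limit. Protocol Table 6 gives the same item a range: "Total Number of Months (0-12").

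SAP Appendix 1 differs. Its only secondary child outcomes are Bayley-IV and HOME. Birth weight and length appear there as perinatal-history items under the exploratory heading, recorded at baseline and 12 months. Its breastfeeding rows cover feeding plan and pain, not duration.

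Women are eligible in pregnancy up to 36 weeks or from 4 to 30 weeks postpartum (SAP Table 1). Perinatal period is a stratification factor (SAP 1.5).

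**The concern.** Taken at its word, the plan tests birth weight, birth length and breastfeeding months between randomised arms in all women. For every postnatal enrolee, birth size was settled before allocation, so no provider or delivery mode could have changed it. Including these women pulls an arm difference towards zero, and a null result could then be read as reassurance.

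Breastfeeding has two separate difficulties. In postnatal enrolees part of the duration, and sometimes all of it, had passed before randomisation. In both strata, a mother still breastfeeding at the visit has no stopping age, so her duration is right-censored at the child's age that day. Neither document says how she is scored. Recorded months therefore depend on visit age as well as on behaviour.

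**Working it through.** **Inputs from the documents.** 393 per group, difference 3.0, SD 15, two-sided alpha 0.05, 80% power, antenatal share s up to 0.75 (all SAP 3.4.2.4); total 1,226 (SAP 1.6.2); enrolment window (SAP Table 1).

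**Assumptions.** A birth-size effect of 0.2 SD in antenatal women, which is the plan's own standardised Bayley effect (3/15), and zero in postnatal women. Breastfeeding durations are exponential with median 6, 9 or 12 months. Visit ages are uniform over stated windows. The documents give none of these distributions.

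**1. The plan's figure.** n = 2(1.960 + 0.842)² × (15/3)² ≈ 2 × 7.85 × 25 ≈ 392.5, rounded up to 393; power at 393 is 80.1%. The stated sample size reproduces.

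**2. Birth size between randomised arms.** The average effect over all women is s × 0.2 SD. Power is Φ(d√(n/2) − 1.96), and the required n grows as 1/s². At s = 0.75, d = 0.15 and 0.15 × √(393/2) = 2.10, so power is Φ(0.14) = 55.7%. The last two columns assume 1,226/2 = 613 per arm (SP vs NSP, everyone contributing).

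| Antenatal share | Average effect | Power, 393 per arm, all women | n per arm for 80% | Power, 613 per arm, all women | Power, antenatal women only |
|---|---|---|---|---|---|
| 75% | 0.15 SD | 55.7% | 698 | 74.7% | 85.8% (about 460 per arm) |
| 50% | 0.10 SD | 28.8% | 1,570 | 41.7% | 69.7% (about 306 per arm) |

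Restriction gains power in general. The signal-to-noise ratio is s·d·√(n/2) with all women and d·√(s·n/2) with antenatal women only, a gain of 1/√s (1.15 at s = 0.75). Under no effect, both tests hold their level.

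**3. Breastfeeding already elapsed at postnatal enrolment.** 4/4.345 = 0.9 months and 30/4.345 = 6.9 months; the latter is 58% of a 12-month range. With medians of 6 to 9 months, 7–10% have stopped by 4 weeks and 41–55% by 30 weeks (1 − exp(−Lt), L = ln 2/median).

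**4. Censoring.** If a mother still breastfeeding is scored at the child's current age, mean recorded months at visit age t are (1 − exp(−Lt))/L. The last four columns come from simulation. Those on false positives use 393 per group with identical breastfeeding behaviour in both groups; 'different' visit ages means 6–18 vs 9–24 months.

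| Median | Mean at 6 / 12 / 24-month visit, no cap | Still breastfeeding at visit, ages 6–24 | False positives, same visit ages (no cap / 12-month cap) | Different visit ages, no cap | Different visit ages, 12-month cap |
|---|---|---|---|---|---|
| 6 | 4.3 / 6.5 / 8.1 | 21% | 4.1% / 5.8% | 71.0% | 28.0% |
| 9 | 4.8 / 7.8 / 10.9 | 34% | 5.8% / 3.8% | 97.0% | 52.6% |
| 12 | 5.1 / 8.7 / 13.0 | 44% | 5.0% / 5.4% | 99.8% | 66.8% |

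With a 12-month cap and visits uniform over 6–24 months, the mean falls short of the true capped mean by only 0.3 to 0.6 months (6.17 vs 6.49, 7.36 vs 7.83, 8.10 vs 8.66). All of that comes from visits before 12 months.

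**5. Could visit ages differ?** The child of a woman enrolled at 30 weeks postpartum is already 6.9 months old, so a 6-month visit is impossible for her but possible for antenatal enrolees. This makes a difference between the antenatal and postnatal groups plausible, without establishing it. Between randomised arms there is less reason to expect one.

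**The case against.** The strongest reply concerns scope. The sentence names two outcomes, mental development and psychosocial stimulation, and times them at 6–24 months, whereas birth size is assessed at birth. Appendix 1 lists only Bayley and HOME as secondary child outcomes. The aim and sample size concern child mental development, and no hypothesis or power is stated for birth size or breastfeeding. Table 2 also carries descriptive variables, so appearing there need not mean being tested. The rule for ongoing breastfeeding may sit in the codebook, which is not in these documents.

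This lowers the priority but does not remove the point. The sentence covers all child outcomes and gives two as examples, SAP 1.4 calls the Table 2 entries outcomes, and nothing excludes birth size or breastfeeding. The disagreement between Table 2 and Appendix 1 itself needs settling.

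The second reply is that visit timing is partly handled. The SAP adjusts the antenatal vs postnatal regression for time since treatment, and Protocol 3.5.2 names child age as a possible covariate in mixed models. Both bear on visit age. Neither turns a censored duration into a complete one.

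A reader might infer that the antenatal vs postnatal contrast in birth size is diluted too. It is not: postnatal enrolees were untreated at the birth, so their values properly represent no treatment. The weakness there is that the groups are not randomised. A reader might also infer that censoring makes every t-test on months wrong. With matching visit ages the simulated error rate stays at about 4–6%, so bias requires visit ages to differ.

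**Conclusion.** The point holds at minor priority. In the SP vs NSP and in-person vs telemedicine comparisons, an effect on birth weight or length shrinks to at most the antenatal share. At the plan's 75% ceiling this costs about 24 percentage points of power for 0.2 SD at 393 per arm (80.1% to 55.7%), and more if fewer women are antenatal. These tests lose power but are not invalid.

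For breastfeeding, a t-test on months loses information whenever mothers are still breastfeeding at the visit, and is biased if visit ages differ between groups. The bias is smaller under the Protocol's 0–12 range than under the SAP's open one. Its size rests on assumed durations, visit windows and scoring.

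A reader might take this as undermining the child-development aim. The documents do not support that: Bayley, HOME and the 393-per-group calculation are unaffected.

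**What to change.** In SAP 3.4.2.4:

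1. State which child outcomes each comparison covers, and bring Table 2 and Appendix 1 into agreement.
2. Compare birth weight and length between randomised arms in the antenatal stratum only. Treat them as baseline characteristics in postnatal enrolees, and describe any antenatal vs postnatal contrast as non-randomised.
3. Replace the t-test on breastfeeding months with time to stopping: age at stopping is the event, and the child's age at the visit is the censoring time. In the arm comparisons, postnatal women still breastfeeding at randomisation enter at infant age at randomisation, and those who had already stopped do not contribute. A simpler alternative is breastfeeding status at 6 months, an age every child has reached by the visit, with arm comparisons limited to antenatal women.
4. Reconcile the Protocol's 0–12 range with the SAP. Drop the limit only if the time-to-event analysis is adopted; under a t-test, dropping it would enlarge the bias when visit ages differ (28–67% false positives become 71–100% in the example above).

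The cost is SAP wording and one different procedure, using the child's birth date and age at stopping, which the plan already lists, and the visit date, which should be on record. The downside is fewer women in the birth-size arm comparisons (613 to about 460 per arm at 75% antenatal), more than repaid in power (74.7% to 85.8%).

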#### 2.8. Randomization

All participants will be stratified by perinatal period (antenatal vs. postnatal) and then randomized within site to one of the four arms, unless restricted to two arms due to COVID-related institutional restrictions of in-person care (see section 2.2.3.2) and using a web-based randomization service as part of REDCap™. Randomization will occur only after informed consent has been obtained and all baseline measures have been completed and all inclusion/exclusion criteria verified with the participant. We will enroll equal numbers in each of the four intervention arms. This strategy allows sufficient power to determine whether NSPs are no less efficacious than specialists and telemedicine is no less efficacious than in-person treatment, respectively, in settings that collectively assure ethnic and racial diversity, as well as potential heterogeneity in age, variability in symptom severity as well as access to resources.

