1.3. Eligibility Criteria

1.3.1. Trial Participants

Pregnant and postpartum women[†] are recruited from three study Hubs (Toronto, Chapel Hill, Chicago) through their networks of clinics. In Toronto, we are recruiting from three sites: Sinai Health, Women's College Hospital and St. Michael's Hospital (referrals-only site). In the US, we are recruiting from the University of North Carolina in Chapel Hill, and NorthShore University HealthSystem in Evanston and surrounding areas including Chicago. Inclusion and exclusion criteria are detailed in [Table 1](#).

Table 1: Inclusion and exclusion criteria

INCLUSION	EXCLUSION

 EPDS\geq10 \geq18 years Pregnant up to 36 weeks or 4 to 30 weeks postpartum Speaks English or (US sites) Spanish 	
 Active suicidal intent (ideation and plan), active symptoms of psychosis or mania Psychotropic medication dose or medication change within two weeks of enrollment or beginning treatment Ongoing psychotherapy (no more than once every 8 weeks or during the duration of the intervention) Active substance abuse or dependence Severe fetal anomalies, stillbirth or infant death at time of enrollment for index pregnancy Non-English, non-Spanish speakers

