1.5. Randomization

All SUMMIT participants are stratified by perinatal period (antenatal vs. postnatal) and were initially (Phase 1) randomized within site to one of four arms (see [Figure 2](#)). However, during the early part of the COVID-19 pandemic (Phase 2) when in-person care was prohibited, participants were randomized to only one of two arms: TM NSP and TM SP ([Figure 2](#)). All sites resumed randomization to all 4 arms 16 months later (Phase 3). Given that Phase 2 consisted of

Figure 2. Randomization strategy

*Randomization can shift to the two telemedicine arms based on site specific, COVID-related institutional restrictions, and once enrollment to in-person arms is complete.

randomizing participants exclusively to TM, there was an imbalance in participant assignment between the IP and TM arms. To address this, a weighted randomization approach (3:1, favoring IP) was used in Phase 3 in which a reduced percentage of

participants were randomized to the TM arms to ensure that the study's sample size targets will be met, and the final sample has an equal number of IP and TM participants. Due to the Omicron wave in December 2021 and January 2022, participants were randomized to TM-only again and randomization switched back to a 1:1 ratio. However, sites were permitted to switch between a 1:1 TM-only (2 arm) and a 1:1:1:1 both TM and IP (4 arm) randomization scheme based on site-specific COVID restrictions and Infection Prevention and Control (IPAC) recommendations. Sites began resuming Phase 1 randomization to IP in the 1:1:1:1 ratio in January 2022, and all sites returned to Phase 1 randomization by April 2022. Randomization to all 4 arms will be followed until in-person arms are fully enrolled after which randomization 1:1 to the two telemedicine arms will be followed.

Table 2: SUMMIT Outcomes (A more detailed list can be found in [Appendix 1](#)).

Study Variable	Instrument	Outcome (Range)
Maternal: Measured at Baseline and 3*-, 6*- and 12*-months post-randomization		
Maternal Characteristics**	Trial Baseline Questionnaire ^{6,7}	Self-reported age, education level, gender identity and sexual orientation, marital status, immigrant status and ethnicity, clinical history with depression or anxiety (severity, chronicity, number of prior episodes, and age at first episode), occupational status, number of children, pregnancy intention, pregnancy history, delivery and birth.

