3.4.2.5. Analysis for Secondary Aim 3: Perinatal Period and Perinatal Depression and Anxiety

We are also **exploring whether the timing of the treatment (antenatal vs. postnatal) influences depressive and anxiety symptoms at 12-months post-randomization.**

This model will also test whether expectant mothers who receive antenatal treatment benefit more in terms of reduced depressive symptoms than mothers who receive postnatal treatment at 12-months post-randomization. A 2-group comparison with at least 200 per group and an assumed mean of EPDS score of 7.93 (SD=4.68)³⁰ will provide 90% power, with an alpha of 0.05, to detect a mean change of 1.5 points. This allows us to detect a drop corresponding to a small effect size of 0.3 (i.e., a drop to mean 6.43 on the EPDS). The two groups' (antenatal vs. postnatal) EPDS scores at 3-months will be compared using a two-sided two-sample t-test. An exploratory analysis will be carried out on this set of patients to test for a group by treatment interaction at 12 months.

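### Antenatal versus postnatal timing is not randomised, and the SAP names no maternal baseline confounder for that comparison

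*SAP*

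**What the plan says.** **How women enter the two groups.** Protocol 2.8 states: "All participants will be stratified by perinatal period (antenatal vs. postnatal) and then randomized within site to one of the four arms". SAP 1.5 likewise treats perinatal period as a stratum. The group follows from eligibility at enrolment (SAP Table 1): "Pregnant up to 36 weeks or 4 to 30 weeks postpartum".

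**Child outcomes (SAP 3.4.2.4).** The aim reads: "Another secondary aim is to explore whether the timing of the treatment (antenatal vs. postnatal) influences child mental development". The hypothesis concerns mothers "who receive the antenatal treatment will benefit more in terms of improved child outcomes at 6-24 months than mothers who receive postnatal treatment". The named test is that outcomes "will be compared between two groups (antenatal vs. postnatal) at 6-24 months post childbirth using a two-sample two-sided t-test". A second t-test is named for raw and standardised Bayley scores at 12 months. The same section adds: "We will adjust for time since treatment by including it as a variable in the regression model comparing antenatal vs. postnatal".

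**Maternal symptoms (SAP 3.4.2.5 and 3.4.2.2).** Section 3.4.2.5 will test whether "expectant mothers who receive antenatal treatment benefit more in terms of reduced depressive symptoms than mothers who receive postnatal treatment" at 12 months. The t-test it names is on EPDS at 3 months. Section 3.4.2.2 plans linear mixed models for EPDS and GAD-7 over baseline, 3, 6 and 12 months with a group-by-time term; it lists no covariates.

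**Elsewhere.** SAP 1.2 says that site will be considered as a possible covariate in all analyses. Protocol 3.5.2 lists baseline depression, medication, treatment dosage and (for child outcomes) child age as possible covariates in its mixed models. Protocol 3.5.3.2 plans covariate control, including child age, for 12-month anxiety.

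**The concern.** Stratified randomisation balances provider and mode within each perinatal period. It does nothing to make antenatal and postnatal women comparable with each other. They may differ in symptom severity, psychiatric history, parity, site mix and the phase of the pandemic in which they enrolled. A two-sample t-test attributes all such differences to timing.

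The hypotheses are nevertheless worded causally: timing influences outcomes, and antenatal treatment yields the greater benefit. Neither document says that this contrast is not randomised. If the SAP is followed as written, a difference between two kinds of women could be reported as an effect of treating earlier, and that would bear on when services offer treatment.

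**Working it through.** **1. What each planned analysis of timing contains**

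| Place | Analysis | Covariates named |
|---|---|---|
| SAP 3.4.2.4 | t-test, child outcomes, 6-24 months | none |
| SAP 3.4.2.4 | t-test, Bayley, 12 months | none |
| SAP 3.4.2.4 | regression, antenatal vs postnatal | time since treatment |
| SAP 3.4.2.5 | t-test, EPDS, 3 months | none |
| SAP 3.4.2.5 | unspecified model, EPDS, 12 months | none |
| SAP 3.4.2.2 | mixed models, EPDS and GAD-7 | none (baseline is a time point) |
| SAP 1.2 | all analyses | site, to be considered |

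The rule in SAP 3.4.1 to adjust for variables imbalanced at baseline follows the text on Aims 1 and 2. The baseline comparisons that section plans are between modes and between provider types. Nothing extends either to timing.

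**2. The plan's own figures**

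- Bayley (difference 3.0, SD 15, two-sided alpha 0.05, 80% power): n = 2 × (1.96 + 0.8416)² × 15² / 3² = 392.4, so 393 per group. This matches the SAP.
- EPDS (200 per group, SD 4.68, difference 1.5): SE = 4.68 × √(2/200) = 0.468; power = Φ(1.5/0.468 − 1.96) = 89.3%, against a stated 90%.

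The arithmetic is sound. The issue is what the test estimates.

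**3. What an uncontrolled difference would do (assumed values)**

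With no true timing effect and a confounding bias b, P(significant) = 1 − Φ(1.96 − b/SE) + Φ(−1.96 − b/SE).

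| Outcome | SE | b | P(significant) |
|---|---|---|---|
| EPDS, 200 per group | 0.468 | 0 | 5% |
| | | 0.3 | 10% |
| | | 0.5 | 19% |
| | | 1.0 | 57% |
| Bayley, 393 per group | 15 × √(2/393) = 1.070 | 0.5 | 7.5% |
| | | 1.0 | 15% |
| | | 2.0 | 46% |

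A bias of 0.3 to 0.5 EPDS points would arise if the groups differed by 1 point at screening and the slope of follow-up on screening EPDS were 0.3 to 0.5: 1 × 0.3 to 0.5 = 0.3 to 0.5, or 20% to 33% of the 1.5-point target. Both inputs are assumptions. The illustration applies to a raw follow-up t-test, not to the mixed models or the regression.

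**4. Why time since treatment cannot stand in for confounders**

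Count time T from enrolment (a simplification). A child whose mother enrolled g weeks before birth is aged T − g. A child whose mother enrolled p weeks after birth is aged T + p, with p between 4 and 30 by eligibility. At equal T, the postnatal child is older by g + p, which is more than 4 weeks. At equal child age, the antenatal mother has the longer interval by the same amount. The covariate is thus partly determined by the timing group. Holding it fixed while omitting child age sets the groups apart on child age.

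**5. The precision cost of adjustment**

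If the timing group has multiple correlation R with the covariates, the variance is multiplied by 1/(1 − R²). With the SD kept at 15 and no credit for covariates that explain the outcome:

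| R | Factor | n per group for 80% power | Power at 393 |
|---|---|---|---|
| 0.3 | 1.10 | 432 | 76% |
| 0.5 | 1.33 | 524 | 68% |
| 0.7 | 1.96 | 770 | 52% |

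**The case against.** The other side has several good points.

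- **The plan is not confined to unadjusted t-tests.** A reader might infer that it is. The documents do not support that: there is the regression in SAP 3.4.2.4, there are the mixed models in 3.4.2.2 with baseline as a time point, and SAP 1.2 brings in site. The protocol names further covariates. This stands and narrows the point to what is missing: maternal baseline confounders in the SAP's timing sections.
- **The 12-month depression hypothesis is not tied to the t-test.** In SAP 3.4.2.5 the hypothesis is at 12 months and the t-test at 3 months. It would be wrong to say that the claim of greater benefit for depression rests on that t-test. The model meant for 12 months is simply not specified.
- **Confounding is not demonstrated.** All women meet the same EPDS entry threshold, and no document reports an imbalance. This stands: the comparison is open to confounding, not shown to be confounded. A common threshold does not equalise severity above it, or history, parity or phase.
- **The aim is secondary and worded as exploratory.** That limits the weight of the point. It does not make a causal reading of an observational contrast valid.
- **Adjustment can go wrong.** Number of children at baseline includes the index child for postnatal women unless defined otherwise, so it would partly encode the exposure. The fix below allows for this.

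**Conclusion.** The point holds in a limited form. Secondary Aim 3 is an observational comparison. The tests named for child outcomes and for 3-month EPDS have no covariates, and the models planned beside them name no maternal baseline confounder. The protocol's fuller list is not carried into the SAP's timing sections.

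A reader might go further and conclude that the result is biased by a known amount, for example 20% to 33% of the target difference. The documents give no basis for that. The figures in the working show only that modest biases would matter at these sample sizes, and they rest on assumed inputs.

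The weight is moderate at most. The randomised comparisons of provider and mode, including those planned for child outcomes, are not affected.

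**What to change.** Amend SAP 3.4.2.2, 3.4.2.4 and 3.4.2.5 as follows.

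- **Main analysis.** Use a regression for child outcomes and the planned mixed models for EPDS and GAD-7, stating which model tests the 12-month hypothesis. Keep the t-tests as descriptive.
- **Pre-specified covariates.** Screening EPDS and GAD-7, site, randomisation phase, age, education, prior depression or anxiety, and births before the index child. In the EPDS and GAD-7 mixed models the screening score can enter as the baseline time point instead.
- **Child outcomes.** Add child age at assessment. Reconsider time since treatment, for instance as a sensitivity analysis only.
- **Reconcile with Protocol 3.5.2 and 3.5.3.2.** Say which of their covariates apply. Treatment dosage is recorded during treatment, so it is not a baseline confounder.
- **Wording.** State that timing was not randomised, and report an association rather than a greater benefit of antenatal treatment.

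The cost is SAP text. SAP Appendix 1 shows that the questionnaire items are collected, and site and phase are known from randomisation. Births before the index child must be derived so that the index birth is not counted. Adjustment may cost precision where covariates track timing (working, step 5), partly offset where they explain the outcome. Unmeasured differences will remain, which is why the wording matters as much as the model.
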